13.0 Risks to Participants

13.1 Foreseeable Risks: Potential risks of losartan are detailed in consent forms. The most severe risks of losartan use include teratogenicity in the setting of pregnancy, hypersensitivity including angioedema, symptomatic hypotension, worsening of renal function, and electrolyte abnormalities. The most common side effects of losartan include fatigue, weakness, diarrhea, chest pain and anemia. Subjects will be rigorously screened to ensure that they are at low risk for complications due to

losartan and they will be monitored closely for side effects and signs of toxicity. The package insert for Losartan has been included with this protocol. Clinical trial and post-marketing surveillance data (see package insert) demonstrate an excellent safety profile. In over 4,000 patients, there was a low incidence of adverse events (2.3%) comparable to placebo (3.7%). The effects more common in losartan than placebo were clinically minor, including dizziness (3% vs 2%), upper respiratory infection (8% vs 7%), nasal congestion (2% vs 1%) and back pain (2% vs 1%). While losartan has the potential to cause symptomatic hypotension, four studies have identified losartan has a negligible effect on resting blood pressure and heart rate in healthy volunteers.³⁴⁻³⁷ It has been theorized there may be an increase risk of cardiac dysfunction in patients taking an ACE-I or ARB in COVID-19, though evidence for this effect is lacking. In fact, the most recent preprinted (non-peer reviewed) data from China now suggest a protective effect based on retrospective data compared to other antihypertensive regimens. However, this will be monitored carefully through admission rates and AE/SAE reporting to the DSMB, in addition to continuous monitoring of the primary outcome by the DSMB.

- 13.2 *Reproduction Risks:* Losartan is class D in pregnancy. Women of childbearing age will only be eligible for enrollment with a negative pregnancy test prior to enrollment. In addition, women breastfeeding will be excluded from the study.
- 13.3 *Risks to Others:* The primary risk to others is the risk to study personnel of becoming infected with COVID-19. To overcome this barrier, patients will be enrolled using an electronic consent process already established among our group for other studies. In addition, follow-up evaluations will preferentially be performed by phone. If a face-to-face evaluation or physical examination is required due to concern for adverse events, participants will be directed to a clinic or emergency department that is prepared for management of patients with COVID-19, and instructed on techniques to minimize exposure of others. Participants will generate potential biohazards (oropharyngeal swabs), the safety steps surrounding which are discussed in section 6.2.

14.0 Potential Benefits to Participants

- 14.1 *Potential Benefits:* If randomized to the intervention arm, and if losartan is demonstrated to prevent the progression of acute lung injury, patients may benefit by having reduced lung injury, decreased need for oxygen or mechanical ventilation, or possibly lower mortality. If randomized to the control arm, there is no direct potential benefit to the patient. However, the proposed research has the potential to significantly benefit people infected with COVID-19.

15.0 Statistical Considerations

- 15.1 *Data Analysis Plan:* All analysis will focus on comparisons between the treatment and control groups. Demographics and other baseline clinical characteristics will be summarized using descriptive statistics. Descriptive statistics will be presented by treatment group using mean, standard deviation, median, and interquartile range (IQR) for continuous variables and frequencies and percentages for categorical variables. The primary outcome, hospitalization at day 15, will be summarized by group using the sample proportion with 95% asymptotic confidence intervals. Treatment groups will be compared using the Chi-square test and the treatment

effect will be summarized by the absolute difference in the hospitalization rate between groups. Secondary endpoints will be summarized by the mean and standard deviation and compared using the two-sample unequal variance t-test, potentially after appropriate data transformations to assure that assumptions of the t-test are met. Time-to-event endpoints will be summarized by Kaplan-Meier curves and compared using Cox proportional hazards regression. For all endpoints, we will complete secondary analyses comparing for important baseline variables that are unequally distributed between treatment groups. Preplanned subgroup analyses are planned by age (dichotomized at 50 and by decade), history of hypertension, sex, and smoking history, timing of randomization from symptom onset, and respiratory support needed at the time of randomization. In addition, we will perform a preplanned pooled analysis with a planned national outpatient trial of losartan versus placebo targeting the same patient population with harmonized assessments and outcomes.

15.2 *Power Analysis:* Previously published literature from China suggest a 15% hospitalization rate for patients infected with coronavirus.^{7,30} To detect a difference in hospital admission rate of 15% in control vs. 7% in the intervention group, with alpha of 0.05 and 80% power using a two-sided test, we will need 264 patients in each group. We will enroll a total of 290 patients in each group (total sample size of 580) to account for the possibility of 10% loss-to-follow-up.

15.3 *Data Integrity:* The principal investigator will manage oversight of quality control for collected data. Recruitment of subjects will be performed using inclusion/exclusion criteria defined above. Study data will be recorded within a RedCAP database, which is HIPAA compliant, password protected with variable assignable security access and an audit trail consistent with all regulatory requirements for maintenance of clinical trial data. Data summaries and quality control checks will be run routinely.

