 - Patient-collected oropharyngeal swabs will be retrieved using a courier service with capacity for transport of biologic specimens to a BSL-3 laboratory (<https://www.researchservices.umn.edu/services-name/biosafety-level-3-program>). These will be stored for public health and viral research purposes.
 - Patients will be followed for 90 days to determine outcomes and the presence of any delayed adverse events. Follow-up phone contact and

electronic medical record review will determine the primary and secondary efficacy endpoints, and provide additional safety data.

1.6 *Data and specimen collection method*

- Inclusion and exclusion criteria, patient demographics, baseline comorbidities, symptoms, and validated symptom assessment measurements by patient self-report, obtained in the medical record, or obtained during an in person pre-screening visit will be collected at the time of enrollment and maintained in a RedCap database. In addition, electronic consent forms will be maintained in a University of Minnesota RedCap database with established functionality currently used by our group for this purpose in our group. The database, with the currently approved eConsent policy, and is HIPAA compliant.
- Every other day follow-ups will be recorded by study personnel into a RedCap database and will include self-reported AEs and medication adherence and maximum daily temperature. On days 0, 4 and 10, a previously validated patient-reported outcomes measurement information system (PROMIS) dyspnea survey and SF-12 (survey's attached in supplement). In the event the patient is not available or contacted on the day of survey administration, surveys administered +/- 1 day will be considered before this data point is considered missing. The following datapoints will also be collected, if available:
 - Name
 - Date of birth
 - Medical record number (if applicable)
 - Phone number
 - Email address
 - Age
 - Gender
 - Race
 - Ethnicity
 - Insurance status (if available)
 - Zip code
 - Location of initial sample collection for diagnosis
 - Location of assessment
 - Date and time of initial sample collection for diagnosis
 - Date and time of positive test result for COVID-19
 - Date of first symptoms
 - Date of first fever (temperature >101.5)
 - Vital signs at presentation (if recorded)
 - Clinical laboratory results at presentation (if recorded)

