4.3 *Investigational new drug.* The study will undergo pre-IND review with the Food and Drug Administration to determine the need for an investigational new drug assessment, and will be assigned an IND number if required.

4.4 *Timing of the intervention:* Treatment will continue for 10 days or attainment of the primary outcome (hospital admission).

4.5 *Duration of study participation:* The final follow-up will occur at 90 days after randomization to determine episodes of delayed hospitalization. Data analysis is expected to be completed within 1 year of enrollment of the final patient.

4.6 *Drug Handling, blinding, and randomization:*

Fairview Investigational Drug Services (IDS), part of M Health Fairview will oversee the preparation of treatment drug and placebo. Identical pills (#20) will be placed in identical

MEDICAL PROTOCOL (HRP-590)

SHORT PROTOCOL TITLE: Randomized control trial of losartan for outpatients with COVID-19

VERSION DATE:5APR2020

bottles with a deidentified study number coded by site and patient number (e.g. 01-001, 02-001, etc.). A site-specific randomization schema will be created (each site will undergo permuted block randomization with random block sizes stratified by site and age). Given significant differences in outcome by age, patients will be randomized by age strata (≥ 50 , < 50). Randomization allocation will be 1:1. IDS will not be blinded to patient randomization. All other members of the study, the participants, and the clinical care team will be blinded to treatment allocation.

4.7 *Provision of study drug to patients*: Following randomization, a courier service will ship drugs to study participants within 24 hours of randomization. Each dispensing will contain 20 capsules, enough to complete the 10-day therapy

4.8 *Study unblinding*: MHealth Fairview, East bank Inpatient Pharmacy UMMC campus, will hold the blind for all subjects on study. In the event of an emergency and unblinding is necessary, study staff can contact [contact], option 1, then option 2. This information is included on each label.

4.9 *Biosafety*: N/A. The intervention is not a biohazard.

4.10 *Stem Cells*: N/A

4.11 *Fetal Tissue*: N/A

4.12 *Use of radiation*: N/A

4.13 *Use of Center for Magnetic Resonance Research*: N/A

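### Randomization is stratified by age because age is prognostic, but the primary Chi-square ignores the age stratum and the adjustment rule tends to miss it: valid test, minor and cheap precision gain

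*Combined protocol and SAP*

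**What the plan says.** Protocol section 4.6 sets the allocation: "each site will undergo permuted block randomization with random block sizes stratified by site and age". It gives the reason for the age factor: "Given significant differences in outcome by age, patients will be randomized by age strata", with the cut at 50 years and 1:1 allocation.

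Section 15.1 gives the primary analysis of hospitalization at day 15: "Treatment groups will be compared using the Chi-square test". The treatment "effect will be summarized by the absolute difference in the hospitalization rate between groups". Neither stratification factor is named there. Confidence intervals are promised for each arm's proportion, and none is stated for the difference.

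Age appears again only for subgroups: "Preplanned subgroup analyses are planned by age (dichotomized at 50 and by decade". For every endpoint, "we will complete secondary analyses comparing for important baseline variables that are unequally distributed between treatment groups". The verb in that sentence is unclear, and I read it as covariate adjustment. It comes with no variable list, no threshold and no named decision-maker.

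Section 15.2 sizes the trial for 15% against 7%, two-sided 0.05 and 80% power: "we will need 264 patients in each group". No section specifies a stratified or adjusted primary analysis.

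**The concern.** Blocking on a prognostic factor makes the arms more alike than chance would. An unstratified test does not know this. It estimates its error as if the age mix could differ freely between arms, so the error term is too large and the test rejects slightly too seldom. The design has already paid for the precision, and the analysis does not collect it.

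The adjusted analyses do not make up for this. A rule that selects variables because they look unequal will tend to omit the 50-year stratum, which the blocks keep equal, although it is the one variable the protocol calls prognostic. The rule also leaves the adjusted results to a judgement made after the data are seen. It does not touch the primary p-value.

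**Working it through.** **Inputs from the documents.** 15% control and 7% losartan, two-sided alpha 0.05, 80% power, 264 per arm (section 15.2); 1:1 blocks stratified by site and age (section 4.6).

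**Assumed, because the documents do not give them.** Risk of hospitalization at 50 and over relative to under 50: ratio 1 to 6. Share aged 50 or over: 30% to 50%. Treatment risk ratio 7/15 in both strata.

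**1. The plan's own figure.** With mean rate 0.11, the pooled-variance formula is n = [1.96√(2 × 0.11 × 0.89) + 0.8416√(0.15 × 0.85 + 0.07 × 0.93)]² / 0.08² = (0.867 + 0.369)² / 0.0064 = 238.9. The continuity-corrected version is (n/4)[1 + √(1 + 4/(n × 0.08))]² = 263.4, so 264. The stated figure is reproduced only with the correction. Section 15.1 does not say which Chi-square will be used.

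**2. Direction and size under the null.** With share w aged 50 or over, the under-50 rate is 0.15/[1 + w(ratio − 1)]. The age component of the outcome variance is w(1 − w)(difference in rates)². Blocking removes it from the comparison, but the unstratified test keeps it. Take w = 0.4 and ratio 4. The rates are 0.15/2.2 = 6.8% and 27.3%, and the component is 0.24 × 0.2045² = 0.0100, against a total of 0.15 × 0.85 = 0.1275. The true variance is therefore 92.1% of what the test assumes. The statistic has standard deviation √0.921 = 0.960, and the approximate type I error is 2[1 − Φ(1.96/0.960)] = 4.1%.

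**3. Simulation.** Two strata with exact balance, 264 per arm, 40% aged 50 or over, 400,000 trials per cell, both tests without continuity correction:

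| Age risk ratio | Chi-square type I error | CMH type I error | Chi-square power | CMH power | Gain (points) |
|---|---|---|---|---|---|
| 1 | 5.13% | 5.03% | 84.64% | 84.55% | −0.1 |
| 2 | 4.77% | 4.94% | 84.76% | 85.08% | 0.3 |
| 3 | 4.49% | 4.98% | 85.01% | 85.83% | 0.8 |
| 4 | 4.23% | 5.03% | 85.35% | 86.60% | 1.2 |
| 6 | 3.81% | 5.07% | 85.68% | 87.52% | 1.8 |

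CMH is the age-stratified Cochran-Mantel-Haenszel test. Over shares of 30% to 50%, the gain is 0.3 points at ratio 2, 0.7 to 0.9 at 3, 1.0 to 1.4 at 4 and 1.4 to 2.3 at 6. At ratio 2 with a control rate of 7.5% to 10% and the same treatment risk ratio, it falls to about 0.1 point.

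**4. The remedy in the planned design.** This check used 580 randomized, 10% random loss, seven assumed sites of unequal size, blocks of 4 or 6, 40% aged 50 or over and 40,000 trials. CMH by age alone holds type I error at 4.8% to 5.1%, with gains close to those above. The Mantel-Haenszel risk difference with Sato variance covers 94.8% to 95.3%. Its interval is 0.7% (ratio 2) to 3.7% (ratio 6) narrower than the unadjusted one.

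**5. The imbalance rule.** In the same design, with shares of 30% to 50%, the arms differ in share aged 50 or over by 1.2 points on average after loss. A gap of 5 points or more arises in about 0.1% of trials, against 20% to 24% under simple randomization. The 5-point mark is chosen here for illustration, since the plan has no threshold. The direction does not depend on it: the age stratum is an unlikely candidate for selection.

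**6. The continuity correction.** At ratio 1 it lowers Chi-square power from 84.64% to 81.19%, about 3.4 points, which is more than ignoring the age stratum costs.

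**The case against.** The strongest reply is that the primary-test half is largely preference. A simple, valid, prespecified test has been chosen, and section 4.6 commits to stratified allocation without promising a stratified analysis. Nothing contradicts anything. The size also rests on assumed inputs: ratio 6 with 30% aged 50 or over means 36% against 6% hospitalization in the control arm, which is extreme, and at ratio 2 the gain is 0.3 points. Results by age at 50 will be reported anyway, as subgroups. All of this stands, and it is why the point is minor. It does not remove the case for a near-free change that follows from the protocol's own reason for stratifying.

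Two further objections limit the remedy. Site is also a stratification factor, but site-by-age cells would be sparse, so the complaint is about age alone. A longer fixed covariate list, or adjusted models for all endpoints, would go beyond what has been shown. The documents do not identify other covariates as prognostic, and the model's room depends on the event count. At 15% against 7% about 264 × 0.22 = 58 events are expected. At a 10% control rate with the same risk ratio there would be about 264 × (0.10 + 0.0467) = 39.

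A reader might infer that the Chi-square is invalid or the trial underpowered. The figures support neither. The error is on the conservative side, and at the planned rates power stays above 80% with or without the continuity correction (81.3% to 82.6% with it, over ratios 2 to 6).

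**Conclusion.** The point holds as a minor, cheap improvement. The primary analysis leaves unused a little precision that the age-stratified design provides: about 0.3 to 1.4 power points, with type I error of about 4.1% to 4.9% in place of 5%, for assumed age risk ratios of 2 to 4. The upper bound explored is 2.3 points, at ratio 6. If age is not prognostic, nothing is forgone. These sizes assume a common treatment risk ratio across ages and 30% to 50% of participants aged 50 or over.

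The second half, that the adjustment rule tends to omit the age stratum, follows from how blocking works and does not depend on the assumed ratios. It concerns prespecification of a secondary analysis. It is no threat to the primary result.

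**What to change.** - **Primary test:** Cochran-Mantel-Haenszel without continuity correction, stratified by the age stratum used at randomization.
- **Effect measure:** Mantel-Haenszel stratified risk difference with 95% confidence interval. This keeps the plan's absolute-difference scale.
- **Sensitivity:** the plain Chi-square, stating whether it is continuity-corrected, plus a newly specified 95% confidence interval for the unadjusted difference.
- **Secondary adjusted analysis of the primary endpoint:** always include age, whatever imbalance is seen. Any further covariates are for the sponsor to name before unblinding.
- **Site:** stratifying by it is optional, because the cells would be sparse.

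The cost is SAP wording, a slightly less transparent test, and about 0.1 power point if age is not prognostic. The sample size is unchanged. No new data are needed, since age is already collected under section 1.6 and the stratum is recorded at randomization. The change should be made before anyone on the analysis side sees unblinded data.

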3.0 Study Endpoints/Events/Outcomes

3.1 *Primary Endpoint/Event/Outcomes:* The primary endpoint is the need for hospital admission at 15 days from randomization.

3.2 *Secondary Endpoint(s)/Event(s)/Outcome(s):*

- Subjective improvement in dyspnea as measured by the dyspnea PROMIS measures (survey attached) at day 0, 4 and 10
- Daily maximum temperature
- Number of emergency department or clinic presentations within 28 days
- Disease severity rating on the *7-point ordinal scale* [Time Frame: Day 7, 15, 28]
 - The *7-point ordinal scale* is an assessment of the clinical status at the first assessment of a given study day. The scale is as follows: 1) Death; 2) Hospitalized, on invasive mechanical ventilation or extracorporeal membrane oxygenation (ECMO); 3) Hospitalized, on non-invasive ventilation or high flow oxygen devices; 4) Hospitalized, requiring supplemental oxygen; 5) Hospitalized, not requiring supplemental oxygen; 6) Not hospitalized, limitation on activities; 7) Not hospitalized, no limitations on activities
- Change in viral load by oropharyngeal swab
- Ventilator free days, oxygen free days
- Need for hospital admission and oxygen therapy at 15 days

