5.4 *Patient follow-up:* Participants will receive phone calls by trained study personnel every other day for the 10 days of the intervention period to monitor for the development of complications including lowest daily blood pressure (measured at least once by home blood pressure cuff provided to the patient and medication compliance. Data will be documented into a Redcap database. The coordinators will have participants complete 2 qualitative surveys at enrollment, day 4, and day 10 (both attached in supplement). Surveys and adverse event assessments conducted within 1 day of the time point will be counted as qualifying and not considered missing. At day 15 (+/- 2 day), patients will be asked to return for repeat research blood draw to include creatinine testing. Patients will be contacted by phone at day 28 (+/- 3 days) and 90 (+/- 3 days) for short and intermediate term outcomes. If there is no follow-up due to lack of patient response, this will be documented and not counted as a protocol deviation.

MEDICAL PROTOCOL (HRP-590)

SHORT PROTOCOL TITLE: Randomized control trial of losartan for outpatients with COVID-19

VERSION DATE:5APR2020

5.5 *Table of events:*

		Study Day																			
	Screening / Enrollment ^{t*}	1	2	3	4	5	6	7	8	9	10	11	12	13	14	15	28	90			
ELIGIBILITY																					
Covid-19 Result confirmation	X																				
Inclusion / Exclusion	X																				
Informed Consent	X																				
ADDITIONAL POST-ENROLLMENT PRESCREENING (IF NOT ALREADY AVAILABLE)																					
Pregnancy assessment and birth control X plan**	X																				
Blood Pressure within 1 week of randomization	X																				
Creatinine / Potassium within 1 week of randomization	X																				
Randomize subject if eligible after additional prescreening	X																				
POST-RANDOMIZATION																					
Demographics	X																				
Medical History / CRF	X																				
Dispense / administer study drug**	X	X	X	X	X	X	X	X	X	X	X										
STUDY PROCEDURES (while outpatient) #																					
Assessment of Hospitalization			X		X		X		X		X								X	X	
Adverse event assessment			X		X		X		X		X								X	X	
Review adherence			X		X		X		X		X										
Review and record blood pressures and temperatures			X		X		X		X		X										
PROMIS Survey					X							X							X		

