Short Form 12 Health Survey						X						X							X		
Oropharyngeal swabs	X			X		X			X		X										
Potassium / Creatinine Check																			X		
Follow-up biospecimens (OP swab + blood draw)																		@			
Electronic medical record / death index review																			X		

*Within 72 hours of + COVID-19 test results,

**In women of child-bearing age, patients must confirm negative test with study personnel prior to beginning treatment as well as confirmation of acceptable birth control method. For those capable of having children, a pregnancy test will be delivered to patients to confirm no pregnancy prior to initiation of study drug.

#Outpatient follow-ups +/- 1 day are accepted.

@ We will attempt to obtain oropharyngeal and blood biospecimens from patients hospitalized when they would otherwise have been planned

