16.4 *Approximate number of records required for review:* 580, BPIC will be used to extract structured data, for unstructured data or patients that are not admitted to the hospital phone calls by study coordinators will collect data which will be manually entered into Redcap.

16.5 *Please describe how you will communicate with research participants during the course of this research. Check all applicable boxes:*

- This research involves record review only. There will be no communication with research participants.
- Communication with research participants will take place in the course of treatment, through MyChart, or other similar forms of communication used with patients receiving treatment.
- Communication with research participants will take place outside of treatment settings. If this box is selected, please describe the type of communication and how it will be received by participants.

16.6 *Explain how the research team has legitimate access to patients/potential participants:* Informed consent will be obtained from patients granting access to clinical data for study participants.

16.7 *Location(s) of storage, sharing and analysis of research data, including any links to research data (check all that apply).*

- In the data shelter of the [Information Exchange \(IE\)](#)

MEDICAL PROTOCOL (HRP-590)

SHORT PROTOCOL TITLE: Randomized control trial of losartan for outpatients with COVID-19

VERSION DATE:5APR2020

Store Analyze Share

In the Bone Marrow Transplant (BMT) database, also known as the HSCT (Hematopoietic Stem Cell Transplant) Database

Store Analyze Share

In REDCap (recap.ahc.umn.edu)

Store Analyze Share

In Qualtrics (qualtrics.umn.edu)

Store Analyze Share

In OnCore (oncore.umn.edu)

Store Analyze Share

In the University's Box Secure Storage (box.umn.edu)

Store Analyze Share

In an AHC-IS supported server. Provide folder path, location of server and IT Support Contact:

Store Analyze Share

In an AHC-IS supported desktop or laptop.

Provide UMN device numbers of all devices:

Store Analyze Share

Other. Describe:

Indicate if data will be collected, downloaded, accessed, shared or stored using a server, desktop, laptop, external drive or mobile device (including a tablet computer such as an iPad or a smart device (iPhone or Android devices) that you have not already identified in the preceding questions

will use a server not previously listed to collect/download research data

will use a desktop or laptop not previously listed

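### PROMIS dyspnea should be analyzed with pre-specified adjustment for its day-0 score, and the plan should say whether the survey continues after hospital admission

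*Combined protocol and SAP*

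**What the plan says.** **Analysis.** Section 15.1 gives one rule for secondary endpoints: "Secondary endpoints will be summarized by the mean and standard deviation and compared using the two-sample unequal variance t-test", with transformation if needed. Its only provision for baseline differences is that "we will complete secondary analyses comparing for important baseline variables that are unequally distributed between treatment groups". No variable is named and no threshold for imbalance is given.

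**Endpoint.** Section 3.2 lists "Subjective improvement in dyspnea as measured by the dyspnea PROMIS measures (survey attached) at day 0, 4 and 10". It does not say whether improvement means the score at a given day or the change from day 0, or which day counts. Section 3.4 gives the dyspnea instrument a supporting role: patient-centered evidence, and added biologic plausibility for losartan.

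**Collection.** Section 5.4 says: "The coordinators will have participants complete 2 qualitative surveys at enrollment, day 4, and day 10". Section 1.6 allows one day either side before a survey counts as missing. Neither mentions admission. In the table of events (5.5), the PROMIS row falls under "STUDY PROCEDURES (while outpatient", and the only note on inpatients concerns specimens: "We will attempt to obtain oropharyngeal and blood biospecimens from patients hospitalized when they would otherwise have been planned". Section 16.4 ties phone calls to unstructured data or to participants who were not admitted. No section says how a PROMIS value due after admission is handled in the analysis.

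**The concern.** A baseline score normally predicts the follow-up score on the same instrument. Adjusting for it removes that part of the variance at no cost, because the trial already collects it. Section 15.1 leaves the adjustment out and leaves open a choice between raw score and change. Change uses the baseline less efficiently than adjustment does and can be less precise than ignoring the baseline altogether. The imbalance clause does not fill the gap: the gain in precision comes from the correlation and does not depend on whether the arms happen to differ at day 0.

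The collection question matters because admission is the primary endpoint and is planned to differ by arm. If surveys stopped at admission, more of the sicker participants would be missing on placebo than on losartan, and data not collected at the time cannot be recovered later.

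**Working it through.** **1. The plan's own figure.** Section 15.2 gives 15% versus 7%, two-sided alpha 0.05, 80% power and 264 per group. With a mean rate of 0.11:

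- n0 = [1.96·√(2·0.11·0.89) + 0.84·√(0.15·0.85 + 0.07·0.93)]² / 0.08² = 239 per group.
- With continuity correction: (n0/4)·[1 + √(1 + 4/(n0·0.08))]² = 264. The stated figure is reproduced.

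The documents give no effect size, SD, correlation or power for PROMIS, so everything below is illustration.

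**2. Precision.** Assumptions: 264 per arm, common SD, correlation r between day 0 and follow-up, and the effect that gives a raw-score comparison 80% power: (1.96 + 0.84)·√(2/264) = 0.244 SD. The variance of the group difference, relative to the raw score, is 1 for the raw score, 2 − 2r for change, and 1 − r² for ANCOVA on day 0.

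| r | Variance: change | Variance: ANCOVA | Power: raw | Power: change | Power: ANCOVA | ANCOVA minus change |
|---|---|---|---|---|---|---|
| 0.3 | 1.40 | 0.91 | 80% | 66% | 84% | 18 points |
| 0.5 | 1.00 | 0.75 | 80% | 80% | 90% | 10 points |
| 0.7 | 0.60 | 0.51 | 80% | 95% | 98% | 2 points |

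Against the raw score the gain is 4, 10 and 18 points. A second set of assumptions, 261 per arm (290 less 10%) and an effect of 0.2 SD, gives the same ordering: raw 63%, change 49/63/84%, ANCOVA 67/75/89%.

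**3. Surveys after admission.** At the planned rates, 0.15·264 = 39.6 and 0.07·264 = 18.5 participants are admitted by day 15.

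Let s be the share of these in hospital on day 10 and D their extra breathlessness in SD. Assume that participants whom losartan spares from admission sit at D/2, and that the remaining losartan participants improve by 0.244 SD. Then:

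- Difference in everyone: 0.04·s·D + (1 − 0.15s)·0.244.
- Difference in those at home: [(1 − 0.15s)·0.244 − 0.04·s·D] / (1 − 0.07s).

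| s | D | Everyone (SD) | At home (SD) | Understated by |
|---|---|---|---|---|
| 0.25 | 1 | 0.245 | 0.229 | 7% |
| 0.25 | 2 | 0.255 | 0.219 | 14% |
| 0.5 | 1 | 0.246 | 0.213 | 13% |
| 0.5 | 2 | 0.266 | 0.192 | 28% |
| 1 | 1 | 0.247 | 0.180 | 27% |
| 1 | 2 | 0.287 | 0.137 | 52% |

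The rows with s = 1 are an upper bound: every 15-day admission has happened by day 10 and nobody has been discharged. The values of s, D and D/2 are all assumed.

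**The case against.** **Adjustment is an efficiency preference.** This stands. Randomization makes the unadjusted t-test valid, and the plan claims no power for PROMIS. A reader might infer an inflated false-positive rate or a biased comparison; nothing in the documents supports that. Section 3.2 speaks of improvement and lists day 0, so change from day 0 is a natural reading. Against change, the gain shrinks to 2 points at a correlation of 0.7. What remains is that 15.1 settles on neither.

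**The imbalance clause might cover day 0.** It could, but 15.1 makes those analyses secondary and gives no trigger, so it is not planned adjustment. For the same reason no power can be assigned to it.

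**Sections 5.4 and 5.5 can be read together.** One gives the days, the other limits them to outpatients. That is fair: this is an ambiguity, not a flat contradiction. The outpatient heading is weak evidence that surveys stop, since it also covers adverse event assessment, which section 18.2 requires through day 15 without exempting inpatients. Section 16.4 is a privacy item, and its allowance for unstructured data does not bar a call to an inpatient. A reader might infer that the plan excludes admitted participants; it nowhere says so.

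**Further inferences that are not supported:**

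- *Day 4 is largely safe.* Section 8.3 allows randomization up to 7 days from symptom onset, and section 4.1 puts average admission at 8 to 9 days. A participant randomized on symptom day 5 to 7 and admitted at the average time is admitted 1 to 4 days later.
- *Temperature needs the same repair.* Section 1.6 records a home reading, which agrees with the outpatient heading. If ward readings are more frequent (an assumption), mixing them in would raise the daily maximum more often in the arm with more admissions.
- *The 7-point scale has the same problem.* Section 15.1 already promises frequencies and percentages for categorical variables, and no loss of power is shown there.

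**Conclusion.** The point holds for PROMIS dyspnea. Section 15.1 does not pre-specify adjustment for a day-0 score that the trial collects. Under the assumptions shown, adjustment gains 2 to 18 points of power over a change score and 4 to 18 over the raw score, with the larger gain over change at low correlation and over the raw score at high correlation. It also closes the choice between those two analyses.

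The handling of PROMIS after admission is a secondary point. The documents are ambiguous, and that admitted participants would go unsurveyed is an inference. If they did, missing data would depend on the primary outcome and, under the assumed severities, would tend to understate a real benefit at day 10. The range of 7% to 52% rests wholly on assumed inputs and shows direction, not an expected size.

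Both parts concern a supportive secondary endpoint. The primary analysis and the sample size are unaffected.

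**What to change.** **Free, wording only.** In 15.1, name as the main analysis of PROMIS dyspnea an ANCOVA or a repeated-measures model of the day-4 and day-10 scores, adjusted for the day-0 score. No new data are needed.

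**Cheap.** Reconcile section 5.4 with the table of events for PROMIS. State that the phone survey is still attempted for admitted participants who are able to answer. Report, by arm and day, how many surveys are missing because of admission or death. The cost is a small number of phone surveys in hospital; ventilated participants will still be missing.
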